## STATISTICAL ANALYSIS PLAN

The design is a prospective, observational trial with two cohorts of 200 patients; one in sinus rhythm and the other in atrial fibrillation.

Data will be expressed as proportions for categorical data and median with quartile range for continuously distributed data.

Loss to follow-up for the primary or secondary endpoints is not anticipated. It is anticipated that monitoring data may not be acquired in some patients. This will be recorded. Missing data will not be imputed. Monitored events will be expressed as a rate per day of monitoring data and per patient regardless of the duration of monitoring.

### Primary endpoint analysis

The primary analysis is the incidence rate of the primary composite endpoint.

We will investigate factors associated with the primary point. Pre-specified variables include: age, sex, NYHA class, body mass index, heart rate measured at examination, left ventricular ejection fraction, presence of calcific aortic or mitral valve disease, left atrial volume, conduction abnormalities on the 12-lead ECG, serum potassium and serum creatinine.

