## **7. STATISTICS AND DATA ANALYSIS**

The design is a prospective, observational trial with two cohorts of 200 patients; one in sinus rhythm and the other in atrial fibrillation.

This should generate in excess of 50 deaths in the year following observation assuming a substantial proportion of patients are enrolled soon after an episode of worsening heart failure. We will investigate which measured variables predict overall mortality, sudden death and out-of-hospital sudden death with a particular focus on electrocardiographic findings. We will investigate mode of death, if necessary, by contacting medical and nursing staff (including the patients GP) who attended the patient around the time of death.

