#### **SAMPLE SIZE AND RECRUITMENT**

The sample size is based on the precision of the estimated prevalence of serious arrhythmia. As this is, surprisingly, virtually unknown for similar contemporary populations we intend to study with the proposed technology, this should be considered a pilot. Assuming the incidence of events is low, medium or high (eg:- 5%, 25% or 50%), 200 patients provides a precision around these estimates of approximately  $\pm 5\%$ ,  $\pm 10\%$  and  $\pm 12\%$  with 90% power.

We aim to recruit this population over 12 months – this will entail enrolling about two patients every working day. Due to the small imposition on the patient, the lack of many exclusion criteria and the potential for referrals from across North-West London we believe this is feasible.

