## ENDPOINTS

### Primary endpoint

1. Identification of an arrhythmia for which there is a Class I or IIa recommendation for treatment with medication or devices
2. Either the above or one or more of the following (expanded endpoint) even if it does not otherwise meet guideline-indication for treatment:-
  - Sinus bradycardia  $\leq 30$ bpm for  $\geq 1$ one minute
  - High-degree atrioventricular (AV) block (3rd degree or Mobitz Type I or II)
  - Pauses lasting  $\geq 3$  seconds (either sinus or AV block)
  - Frequent ventricular ectopy defined as  $>1,000$  ectopic beats per day.
  - Ventricular tachycardia with rate  $\geq 100$  bpm for  $\geq 5$  beats.

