### Secondary endpoint analysis

Secondary analyses include the incidence rate of each component of the primary composite endpoint and their association with the above variables.

Multi-variable models will be developed to investigate associations between the above variables, the components of the primary endpoint and all-cause mortality, cardiovascular mortality and the composite outcome measure.

Data and all appropriate documentation will be stored for a minimum of 10 years after the completion of the study, including the follow-up period.

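### Baseline rhythm defines the two cohorts but is not among the 11 pre-specified model variables, and the plan does not say whether models are fitted within cohort or on all 400 patients

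*Combined protocol and SAP*

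**What the plan says.** Section 7 and the Statistical Analysis Plan both describe "two cohorts of 200 patients; one in sinus rhythm and the other in atrial fibrillation". Sample Size and Recruitment states that "200 patients provides a precision around these estimates of approximately" 5, 10 and 12 percentage points, for event proportions of 5%, 25% and 50%, with 90% power.

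Primary Endpoint Analysis then states: "The primary analysis is the incidence rate of the primary composite endpoint". It does not say whether that rate is per cohort, pooled or both. The same section sets out the factors to be examined: "Pre-specified variables include: age, sex, NYHA class, body mass index, heart rate measured at examination, left ventricular ejection fraction", followed by calcific valve disease, left atrial volume, conduction abnormalities, potassium and creatinine. That makes 11 variables. Heart rate and conduction abnormalities are the nearest to rhythm, but neither is rhythm.

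Secondary Endpoint Analysis reuses the list twice. First: "Secondary analyses include the incidence rate of each component of the primary composite endpoint and their association with the above variables". Second: "Multi-variable models will be developed to investigate associations between the above variables, the components of the primary endpoint and all-cause mortality", continuing to cardiovascular mortality and the composite. Only the endpoint components are added there. One of those components is "Sinus bradycardia".

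Section 7 also says: "We will investigate which measured variables predict overall mortality, sudden death and out-of-hospital sudden death with a particular focus on electrocardiographic findings". That sentence does not confine the mortality predictors to the 11. No section mentions a rhythm term, stratification by rhythm or separate models by cohort.

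**The concern.** The variable that defines the design disappears once the models are described. Recruitment fixes the rhythm mix at 50:50, so rhythm is a strong and deliberately balanced source of difference between patients. Left atrial volume and heart rate are plausible examples of listed variables that differ by rhythm. If event risk also differs by rhythm, a model on all 400 without a rhythm term gives those variables part of the credit for AF versus SR. A reader could then take left atrial volume, say, for a marker of arrhythmia risk when it only marks which cohort the patient came from.

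Sinus bradycardia is a special case. A patient who stays in AF throughout monitoring cannot have it, so the pooled rate depends on the recruitment quota. A pooled association analysis of that component also compares patients who can have the event with patients who cannot.

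**Working it through.** **1. The plan's own precision figure.** Inputs from Sample Size and Recruitment: n = 200, p = 5%, 25%, 50%, power 90%. Two-sided 5% alpha is assumed because none is stated. Half-width = (1.960 + 1.282) × √(p(1−p)/n).

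| n | p = 5% | p = 25% | p = 50% |
|---|---|---|---|
| 200 | 5.0 | 9.9 | 11.5 |
| 400 | 3.5 | 7.0 | 8.1 |
| stated | 5 | 10 | 12 |

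Only n = 200 reproduces the stated points. The study is sized for one cohort, so per-cohort reporting is the natural reading of the primary rate.

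**2. Effect of leaving rhythm out of a model on all 400.** All inputs here are assumptions: logistic model with 11 variables; 200 SR and 200 AF patients; the tested variable and three others differ by d standard deviations (SD) between cohorts; seven are unrelated to rhythm; the tested variable has no effect given rhythm; Wald test at 5%.

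A closed-form approximation shows the mechanism. Rhythm is a 0/1 variable with variance 0.25.
- Share of the rhythm effect picked up by the tested variable: k = 0.25d/(1 + d²), which is 0.100 at d = 0.5 and 0.125 at d = 1.
- Apparent odds ratio per SD: exp(k × ln OR). At OR 2: exp(0.0693) = 1.07 and exp(0.0866) = 1.09. At OR 3: exp(0.110) = 1.12 and exp(0.137) = 1.15.
- Variance of the tested variable given the other three shifted ones: v = 1 + 0.25d²/(1 + 0.75d²), which is 1.053 and 1.143.
- Standard error = 1/√(400 × w × v), where w is the mean of p(1−p) over the cohorts. At SR risk 25% and OR 2, AF risk is 40% and w = (0.1875 + 0.2400)/2 = 0.2138. The standard error is 0.105 at d = 0.5, so z = 0.0693/0.105 = 0.66. The chance of exceeding 1.96 in either direction is then about 10%.

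Simulated false-association rates without rhythm (2,000 replicates per cell):

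| SR risk | d | OR 1 | OR 1.5 | OR 2 | OR 3 |
|---|---|---|---|---|---|
| 5% | 0.5 | 5% | 6% | 6% | 10% |
| 5% | 1 | 5% | 6% | 8% | 12% |
| 15% | 0.5 | 5% | 7% | 9% | 15% |
| 15% | 1 | 4% | 7% | 12% | 23% |
| 25% | 0.5 | 5% | 7% | 10% | 18% |
| 25% | 1 | 5% | 7% | 13% | 27% |

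A repeat with 1,500 replicates at SR risk 25% gave 11% and 14% at OR 2, and 19% and 30% at OR 3. The two runs together span 10-14% and 18-30%. With rhythm in the model the rates are 4-7% across runs, and the apparent odds ratio is about 1.00.

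**3. Sinus bradycardia.** Assume no AF patient converts and 20 SR patients have the event: 20/200 = 10% becomes 20/400 = 5% when pooled. In the same 11-variable model on all 400, a variable with no effect in SR appears associated in 16% (d = 0.5) or 26% (d = 1) of runs, against 5-6% in the SR cohort alone. That uses 20/11 = 1.8 events per variable. At an SR risk of 3% (6/11 = 0.5 events per variable) the pooled figures are only about 6-7% and 9-10%.

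**4. Cost of the rhythm term.** The standard error of a rhythm-related predictor rises by √v: 1.026 at d = 0.5 and 1.069 at d = 1. The simulation gives 1.03-1.05 and 1.07-1.09. With 50 deaths, events per variable go from 50/11 = 4.5 to 50/12 = 4.2, before endpoint components are added.

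**The case against.** The strongest reply is that the plan has a coherent reading with no defect. The SAP opens with two cohorts and the precision fits only n = 200. If every model is fitted within cohort, rhythm is constant there and has no place in a covariate list. The list is also open, and the mortality sentence in section 7 is not limited to it. This stands in part: the plan does not exclude rhythm, and nothing shows that the models will be confounded. But no sentence says the models are fitted within cohort, and the variable that defines the design is left to be added or omitted after the data are seen.

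A second reply is that the plan specifies multivariable models only for mortality and the composite, and that in a self-described pilot an association carried by rhythm is a fair description of the enrolled patients. That is also fair. The simulated error rates assume that the question is association given rhythm, and they depend on the choice of four shifted variables.

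A reader might infer several stronger points that the documents do not support:
- That the only baseline ECG is the latest clinical one. Baseline Assessments also lists the study's own patch recording; what is missing is which of the two assigns the cohort.
- That all 200 AF patients are incapable of sinus bradycardia. No criterion requires permanent AF, so some may be in sinus rhythm during monitoring.
- That the mortality models must not be split by cohort because 25 deaths each would give 25/11 = 2.3 events per variable. The 50 deaths are a first-year floor, and follow-up runs up to 5 years.
- That 16% and 26% are the expected error rates for sinus bradycardia. They rest on an assumed 10% SR risk.

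**Conclusion.** The point holds in a limited form. Baseline rhythm is not pre-specified for any model, and the plan does not say whether the models are within cohort or combined. If the 11 named variables are used on all 400, associations for rhythm-related variables can be partly borrowed from rhythm. The documents give no rates by rhythm, so the size cannot be known. Under the stated assumptions it is nil if risk does not differ by rhythm, small at an AF odds ratio of 1.5, and worth preventing from about 2 upwards. At SR risk 25% the false-association rate is then 10-14%, and 18-30% at an odds ratio of 3. Within-cohort fitting removes it.

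The unstated reporting unit and the unstated cohort-assignment rule are missing detail rather than errors, and the sample-size arithmetic is sound. Because the remedy is cheap, the change should be made, but no stated figure in the plan is wrong.

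**What to change.** In the Statistical Analysis Plan:
1. Report both co-primary endpoints for each 200-patient cohort with 95% confidence intervals. Show any pooled figure alongside, with its 50:50 rhythm mix stated.
2. Include baseline rhythm as a term in every factor and outcome model fitted to the combined 400, or fit the model within cohort where the number of events allows.
3. Report sinus bradycardia among patients with sinus rhythm recorded during monitoring, including AF-cohort patients who convert, as well as overall. Use the first denominator for its association analysis, since a rhythm term cannot be estimated if one cohort has no events.
4. State which recording assigns the cohort (the latest clinical ECG or the study patch) and how a patient whose rhythm changes is classed.

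The cost is SAP wording and one model term. The standard error of a rhythm-related predictor rises by about 3-9%, and no extra patients are needed.

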### Secondary endpoint analysis

Secondary analyses include the incidence rate of each component of the primary composite endpoint and their association with the above variables.

Multi-variable models will be developed to investigate associations between the above variables, the components of the primary endpoint and all-cause mortality, cardiovascular mortality and the composite outcome measure.

Data and all appropriate documentation will be stored for a minimum of 10 years after the completion of the study, including the follow-up period.

## 8. REGULATORY ISSUES

### 8.1 ETHICS APPROVAL

The Chief Investigator has obtained approval from the London - Brent Research Ethics Committee. The study must be submitted for Site Specific Assessment (SSA) at each participating NHS Trust. The Chief Investigator will require a copy of the Trust R&D approval letter before accepting participants into the study. The study will be conducted in accordance with the recommendations for physicians involved in research on human subjects adopted by the 18th World Medical Assembly, Helsinki 1964 and later revisions.

## **8.2 CONSENT**

Consent to enter the study must be sought from each participant only after a full explanation has been given, an information leaflet offered and time allowed for consideration. Signed participant consent should be obtained. The right of the participant to refuse to participate without giving reasons must be respected. All participants are free to withdraw at any time from the protocol treatment without giving reasons and without prejudicing further treatment.

## **8.3 CONFIDENTIALITY**

The Chief Investigator will preserve the confidentiality of participants taking part in the study and is registered under the Data Protection Act.

## **8.4 INDEMNITY**

Imperial College London holds negligent harm and non-negligent harm insurance policies which apply to this study

## **8.5 SPONSOR**

Imperial College London will act as the main sponsor for this study. Delegated responsibilities will be assigned to the NHS trusts taking part in this study.

## **8.6 FUNDING**

[name] is supported by an ESC fellowship. [name] has the resources to cover costs of patch-monitors and statistical analysis.

## **8.7 AUDITS**

The study may be subject to inspection and audit by Imperial College London under their remit as sponsor and other regulatory bodies to ensure adherence to GCP and the NHS Research Governance Framework for Health and Social Care (2nd edition).

## **9. STUDY MANAGEMENT**

The day-to-day management of the study will be co-ordinated through [name]

## **10. PUBLICATION POLICY**

Data ownership rights will lie with the institution. The results will be presented at local, national and international meetings and published in a peer-reviewed journal.

## **Appendix 1. Summary of investigations, treatment and assessments**

	Baseline
Informed consent	X
Demographic Data	X
Symptom Questionnaire	X
NYHA Class	X
Physical Examination	X
6 min corridor walk test (if willing & able)	X
Prolonged ECG (up to 14 days) monitoring	X
Haematology	X (nearest in time clinical result)
Biochemistry	X (nearest in time clinical result)
ECG	X (nearest in time clinical result)
Echo	X (nearest in time clinical result)
